16.51 Primary Endpoint

- 16.511 Definition: The primary endpoint of this trial is the proportion of 4-month progression-free survivors as defined in Section 16.31.
- 16.512 Estimation: The proportion of successes will be estimated by the number of successes divided by the total number of evaluable patients. Confidence intervals for the true success proportion will

be calculated using the properties of the binomial distribution. Additionally, if some patients are lost to follow-up not having been observed for at least 4 months, an estimate and confidence interval for the 4-month progression-free survival rate incorporating censoring will be computed using the method of Kaplan-Meier (1958).

16.52 Definitions and Analyses of Secondary, Exploratory, and Correlative Endpoints

Survival time is defined as the time from registration to death due to any cause. The distribution of survival time will be estimated using the method of Kaplan-Meier (1958).

Progression-free survival time is defined as the time from registration to the earliest date of documentation of disease progression. If a patient dies without a documentation of disease progression the patient will be considered to have had disease progression at the time of their death. In the case of a patient starting treatment and then never returning for any evaluations, the patient will be censored for progression 1 day post-registration. The distribution of progression-free survival time will be estimated using the method of Kaplan-Meier (1958).

A response is defined to be either a CR or PR noted as the objective status. As response rate is a secondary endpoint, confirmation is no longer required per RECIST v1.1. The overall response rate will be estimated in the subset of patients with measureable disease by the number of responses in evaluable patients with measurable disease divided by the total number of evaluable patients with measureable disease. The appropriate confidence interval will be calculated based on the binomial distribution.

Duration of response is defined for all evaluable patients with measurable disease who have achieved a response as the date at which the patient's earliest best objective status is first noted to be either a CR or PR to the earliest date progression is documented. If a patient dies subsequent to the response without a documentation of disease progression, the patient will be considered to have had disease progression at the time of their death. In the case of a patient failing to return for evaluations before a documentation of disease progression, the patient will be censored for progression on day 1 post response or the date of last evaluation (whichever one occurs later). The distribution of

duration of response will be estimated using the method of Kaplan-Meier (1958).

Translational analyses: Given the small sample size, all translational analyses are considered exploratory and no adjustment for multiplicity will be employed. One-sided p-values

≤0.10 are considered statistically significant throughout. Results will be used to design subsequent confirmatory studies (likely as translational components within the subsequent phase III study should this phase II study support the use of this combination in a phase III study).

We consider the analysis of baseline PKCı gene amplification to be the primary analysis (though still exploratory) among the

various translational anlayses. PKCı gene amplification will be evaluated at baseline using the baseline tissue specimen and explored in relation to 4-month progression-free survival and subsequently in relation to other clinical outcomes such as tumor response and adverse event incidence using two-way tables and analyzed using Fisher's exact tests. To estimate power for this primary analysis, we assume that 90% of patients (N=33) will provide a usable sample (i.e., will have gene amplification status for this tissue study). We also assume that 70% of patients (N=23) will have PKC1 gene amplification (Regala et al., 2005b) and that 55% of patients overall will have 4-month PFS. The proportion of patients with 4-month PFS will be compared between patients with tumors with PKC1 gene amplification to patients with tumors without PKC1 gene amplification using a 1-sided α =0.10 Fisher's exact test. We have 86% power to detect a 50% difference in the 4-month PFS rates (70% vs 20%) between gene amplified and gene not amplified groups (calculated using nQuery Advisor 6.01 with the following parameters: α =0.10 1-sided, π 1=0.70, π 2=0.20, n1=23, n2=10).

PKC1 protein expression (using the baseline tissue specimen) will be evaluated at baseline and explored in relation to clinical outcomes such as 4-month progression-free survival, tumor response, and adverse event incidence using two-way tables and box plots and analyzed using Fisher's exact tests or logistic regression methods, as appropriate. Further, the relationship among PKC1 gene amplification and PKC1 protein expression will be investigated using box plots and scatter plots and analyzed using Wilcoxon rank sum tests and Spearman correlation coefficients, as appropriate.

Adverse Events: All eligible patients that have initiated treatment will be considered evaluable for assessing adverse event rate(s). The maximum grade for each type of adverse event will be recorded for each patient, and frequency tables will be reviewed to determine patterns. Additionally, the relationship of the adverse event(s) to the study treatment will be taken into consideration.

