2.2 Secondary

- 2.21 To assess the overall survival in this population in comparison to recent historical controls.
- 2.22 To determine the Adverse Events (AE) profile and safety of the regimen.
- 2.23 To determine the overall response rate, per RECIST criteria, and duration of tumor response in those patients with measurable disease.

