13.0 Treatment/Follow-up Decision at Evaluation of Patient

- 13.1 Patients who are CR, PR, or SD will continue treatment per protocol.
- Patients who develop PD while receiving therapy will go to the event-monitoring phase.
- Patients who go off protocol treatment for reasons other than PD will go to the event-monitoring phase per Section 18.0.

- 13.4 Patients who develop PD in the CNS only should receive resection and/or brain radiationand continue treatment on study after completion of CNS treatment.
- Patients who develop non-CNS PD at any time should go to event monitoring. These patients should be treated with alternative chemotherapy if their clinical status is good enough to allow further therapy.
- 13.6 A patient is deemed *ineligible* if after registration, it is determined that at the time of registration, the patient did not satisfy each and every eligibility criteria for study entry. The patient may continue treatment off-protocol at the discretion of the physician as long as there are no safety concerns, and the patient was properly registered. The patient will go directly to the event-monitoring phase of the study (or off study, if applicable).
 - If the patient received treatment, all data up until the point of confirmation of ineligibility must be submitted. Event monitoring will be required per Section
 - 18.0 of the protocol.
 - If the patient never received treatment, on-study material must be submitted. Event monitoring will be required per Section 18.0 of the protocol.
- 13.7 A patient is deemed a *major violation*, if protocol requirements regarding treatment in cycle 1 of the initial therapy are severely violated that evaluability for primary end point is questionable. All data up until the point of confirmation of a major violation must be submitted. The patient will go directly to the event-monitoring phase of the study. The patient may continue treatment off-protocol at the discretion of the physician as long as there are no safety concerns, and the patient was properly registered. Event monitoring will be required per Section 18.0 of the protocol.
- 13. 8 A patient is deemed a *cancel* if he/she is removed from the study for any reason before any study treatment is given. On-study material and the End of Active Treatment/Cancel Notification Form must be submitted. No further data submission is necessary.

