16.11 Phase I Study

This run-in phase I study is a cohorts of 3 design. For a subject to be considered evaluable for dose-limiting toxicity (DLT) the subject must have received at least one dose of each drug in Cycle 1. If a subject withdraws from the study within the first cycle of treatment for reasons other than adverse events, the subject will be replaced; and only DLTs occurring in Cycle 1 will be used for establishing safety during the run-in phase I study. However, all adverse event data will be summarized in the final analysis. For this run-in phase I study, DLT the study design is defined in Section 7.0. The patients treated at the MTD within the phase I will be included in the phase II efficacy analysis. Safety for all patients (including the patients in the run-in phase I study) will continue to be monitored via the Adverse Event Stopping Rule.

- 16.12 Sample Size: Phase I: The study may involve a maximum of 12 patients (6 for each of 2 dose levels). Phase II: This study will accrue an additional 35 patients to have a total of 41 patients accrued to the efficacy portion of this study (6 patients at the MTD in the phase I portion plus 35 patients accrued during the phase II portion). This includes 10% overaccrual of patients during the phase II portion to allow for cancellation, ineligibility, and major treatment violations (i.e., accrual of 41 patients to have 37 evaluable patients as required in 16.41). Overall: Therefore, overall, the study will accrue a maximum of 47 patients.
- 16.13 Accrual Time and Study Duration: The anticipated accrual rate is approximately 2 patients per month, based on physician estimate. This corresponds to a requirement of approximately 17 weeks to enroll (12 weeks), treat (4 weeks), and evaluate (1 week to submit data) 6 patients. Therefore, the accrual time for the phase I portion will be a maximum of 34 weeks. The overall study duration will be 34 weeks (phase I component) + 70 weeks (accrual of an additional 35 patients) + 16 weeks (4 months to evaluate the primary endpoint) = 120 weeks (about 28 months). The final analysis can begin approximately 28 months after activation, i.e., as soon as the last patient has been observed for 4 months and data have been submitted.

16.14 Operating Characteristics: The following table gives the probability of dose escalation at a single dose level as a function of the true probability of DLT at that level using the cohorts of 3 design described in Section 7.0.

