16.53 Data & Safety Monitoring

- 16.531 The principal investigator(s) and the study statistician will review the study at least twice a year to identify accrual, adverse event, and any endpoint problems that might be developing. The Mayo Clinic Cancer Center (MCCC) Data Safety Monitoring Board (DSMB) is responsible for reviewing accrual and safety data for this trial at least twice a year, based on reports provided by the MCCC Statistical Office.
- 16.532 Adverse Event Stopping Rule (PHASE II ONLY): The stopping rule specified below is based on the knowledge available at study development. We note that the Adverse Event Stopping Rule may be adjusted in the event of either (1) the study re-opening to accrual or (2) at any time during the conduct of the trial and in

consideration of newly acquired information regarding the adverse event profile of the treatment(s) under investigation. The study team may choose to suspend accrual because of unexpected

adverse event profiles that have not crossed the specified rule below.

Accrual will be temporarily suspended to this study if at any time we observe events considered at least possibly related to study treatment (ie, an adverse event with attribute specified as "possible", "probable", or "definite") that satisfy the following:

• if 3 or more patients in the first 20 treated patients (or 10% after 20 patients have been accrued) experience a Grade 4 or higher non-hematologic adverse event.

We note that we will review Grade 4 and 5 adverse events deemed "unrelated" or "unlikely to be related", to verify their attribution and to monitor the emergence of a previously unrecognized treatment-related adverse event.

16.6 Results Reporting on ClinicalTrials.gov: At study activation, this study will have been registered within the "ClincialTrails.gov" website. The Primary and Secondary Endpoints (i.e., "Outcome Measures") along with other required information for this study will be reported on ClinicalTrials.gov. For purposes of timing of the Results Reporting, the initial estimated completion date for the Primary Endpoint of this study is 32 months after the study opens to accrual. The definition of "Primary Endpoint Completion Date" (PECD) for this study is at the time the last patient registered has been followed for at least 4 months.

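### Section 16.52 leaves patients who took study drug but were later found ineligible out of the adverse event rates; define one safety set of all treated patients

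*Combined protocol and SAP*

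**What the plan says.** Section 16.52, under Adverse Events, defines the set for the rates: "All eligible patients that have initiated treatment will be considered evaluable for assessing adverse event rate(s". A patient must be eligible and must have started treatment.

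Section 13.6 makes ineligibility a finding that comes after registration, when "it is determined that at the time of registration, the patient did not satisfy each and every eligibility criteria for study entry". It provides for patients who had already been treated by then: "If the patient received treatment, all data up until the point of confirmation of ineligibility must be submitted". They then move to event monitoring.

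Other parts of the plan set no eligibility condition on safety data:

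- Section 16.11 (phase I) says that "all adverse event data will be summarized in the final analysis", and that safety monitoring covers all patients.
- Section 16.21 tabulates all adverse events in phase I, overall and by dose level.
- The stopping rule in section 16.532 counts events "in the first 20 treated patients", and then uses a percentage once 20 patients have been accrued.

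Safety is a stated secondary goal (2.22): "To determine the Adverse Events (AE) profile and safety of the regimen". Section 16.12 plans for some ineligibility: "This includes 10% overaccrual of patients during the phase II portion to allow for cancellation, ineligibility, and major treatment violations".

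**The concern.** An adverse event rate should describe what happened to the people who were exposed. Section 16.52 applies the same eligibility filter that section 16.31 applies to the efficacy endpoint. For efficacy, that restriction can be argued. For safety, it removes exposed patients on a ground unrelated to exposure.

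The filter may also be related to the outcome. Several criteria concern toxicity risk: blood counts and liver tests in 3.15, and lipids, cardiac history and interstitial lung disease in 3.26. Section 15 lists cytopenias, abnormal liver tests, raised lipids and pneumonitis among the known effects of one or both drugs. A patient who failed one of these criteria could be more likely than others to have the matching event, and that event would be missing from the reported rate.

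There is also a conflict within the plan. A related Grade 4 non-hematologic event in a treated, ineligible patient would count toward suspending accrual but would not appear in the 16.52 rates. For phase I patients, sections 16.11 and 16.21 point to one set and section 16.52 to another. With about 41 patients, one or two omitted severe events change the reported rate visibly.

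**Working it through.** **Who is left out**

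| Patient | Treated? | In the 16.52 set? |
|---|---|---|
| Eligible, treated | Yes | Yes |
| Eligible, treated, major violation (13.7) | Yes | Yes |
| Treated, later found ineligible (13.6) | Yes | No |
| Cancel (13.8) | No | No, rightly |

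Only the third row is a problem. Nothing else in section 16.5 brings these patients back.

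**How many there could be**

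The plan's own figure is "accrual of 41 patients to have 37 evaluable patients as required in 16.41". It reproduces: 37 × 1.10 = 40.7, rounded up to 41. (Dividing instead, 37/0.90 = 41.1, gives 42.) The allowance is 41 − 37 = 4 patients, or 4/41 = 9.8%. It is shared by cancellations, ineligibility and major violations, and only treated ineligible patients are affected, so 4 is the most that the planned allowance implies and the likely number is smaller. The documents give no ineligibility rate.

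**Effect on a rate**

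Let n be the number treated, x the number with a given event, k the treated patients found ineligible, and j the number of those k who had the event.

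- All treated: x/n.
- As written: (x − j)/(n − k).
- The as-written rate is lower than x/n only when j/k is greater than x/n.

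Assumptions, for illustration: n = 41 and x = 4, so the rate on all treated patients is 4/41 = 9.8% (exact 95% CI 2.7 to 23.1%).

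| k | j | Rate as written | Exact 95% CI |
|---|---|---|---|
| 1 | 0 | 4/40 = 10.0% | 2.8 to 23.7% |
| 1 | 1 | 3/40 = 7.5% | 1.6 to 20.4% |
| 2 | 0 | 4/39 = 10.3% | 2.9 to 24.2% |
| 2 | 1 | 3/39 = 7.7% | 1.6 to 20.9% |
| 2 | 2 | 2/39 = 5.1% | 0.6 to 17.3% |
| 4 | 0 | 4/37 = 10.8% | 3.0 to 25.4% |
| 4 | 4 | 0/37 = 0% | 0 to 9.5% |

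With k = 2 the rate can rise by 10.3 − 9.8 = 0.5 percentage points or fall by 9.8 − 5.1 = 4.7. The k = 4 rows use up the whole allowance and are the outer bounds. The possible fall is larger than the possible rise, but which occurs depends on j, which the documents do not give.

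**The case against.** **The direction is not established.** A patient is ineligible for missing any single criterion, and several have no evident link to toxicity: histology or Ras status (3.12), the prior platinum doublet (3.13), the 14-day laboratory window (3.15), willingness to return (3.19b) or to give tissue (3.19c). A reader might infer that the exclusion biases rates downward. The documents do not support that as a general statement: if the ineligible patients have no events, the rate rises. What stands is that it may bias the rates, plausibly downward where the failed criterion concerns toxicity risk.

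**The group is small.** Registration verifies eligibility (6.32), and the 4-patient allowance also covers untreated cancels and major violations. This stands.

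**Patient safety is not compromised.** A reader might infer that toxicity is hidden. It is not. Expedited reporting (10.2), routine submission of Grade 3 to 5 events (10.31), data safety monitoring board review (16.531) and the stopping rule (16.532) set no eligibility condition. What changes is a descriptive table with no test attached.

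**The stopping rule and the tables would differ anyway.** The rule counts only related non-hematologic events of Grade 4 or higher, and it mixes treated with accrued patients. The tables record the maximum grade of every event type. A mismatch between the two outputs is therefore not in itself an error. The objection does not explain why the tables should need an eligibility condition that the rule does without.

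**Ascertainment would be incomplete.** Section 13.6 requires data only up to confirmation of ineligibility, and the event-monitoring schedule in section 18.0 lists no adverse event form. This stands as a limit on the fix. Partial follow-up on an exposed patient is still more informative than none.

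**Conclusion.** The point holds in a limited form. Followed as written, section 16.52 omits treated patients later found ineligible from the adverse event rates and frequency tables, and sections 16.11, 16.21 and 16.532 carry no such condition. The defect lies in the final reporting of a secondary goal; safety oversight during the trial is untouched.

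The effect is probably small and its sign is not fixed. The bounds in the working rest on two assumptions that the documents cannot settle: how many treated patients prove ineligible (taken as 0 to 4, from the planned allowance) and how many of them have the event. The starting count of 4 severe events in 41 is also assumed. The 9.8% against 5.1% contrast is the extreme downward case for two ineligible patients and should not be quoted without its upward counterpart of 10.3%.

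The change is worth making because it removes a possible selection effect and a conflict over which set governs, at almost no cost.

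**What to change.** Replace the sentence in section 16.52 with: *All patients who received at least one dose of either study drug, regardless of eligibility, are evaluable for adverse events.*

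Use this set for the adverse event tables and for the treated-patient count in section 16.532. Add a note that adverse event data on ineligible patients are required only up to confirmation of ineligibility, and report how many such patients are in the tables.

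**Cost:** one sentence and a note. The data up to confirmation are already required by section 13.6. The efficacy set, sample size, significance level and power are unchanged. The small downside is truncated ascertainment in those few patients, which could understate their events slightly.
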